8.4.4 Safety Evaluation

All safety data will be included in the subject data listings. Analyses and summary tables will be based upon the safety population.

AEs will be coded according to the National Cancer Institute Common Terminology for Adverse Events Version 3.0

Incidence of all reported AEs/TEAEs and SAEs will be tabulated. In addition, summary tables will be presented by maximum intensity, drug relationship and AEs/TEAEs associated with premature withdrawal of study medication.

A treatment emergent AE (TEAE) is defined as any AE that occurs during the active phase of the study if:

it was not present prior to receiving the first dose of IMP, or

it was present prior to receiving the first dose of IMP but the intensity increased during the active phase of the study, or

it was present prior to receiving the first dose of IMP, the intensity is the same but the drug relationship became possible or probable during the active phase of the study.

Treatment emergent AEs will be flagged (*) in the AEs listings.

Concomitant medication will be summarised by treatment group and by overall with the number and percentage of subjects receiving concomitant medication by drug class and preferred drug name.

Summary statistics (mean, median, standard deviation (SD) and range as appropriate) by treatment group and by overall will be presented for vital signs, clinical laboratory tests at each assessment with change from baseline. For

laboratory data, abnormal values will be flagged in the data listings and a list of clinically significant abnormal values will be presented. Tables will be presented of the number and percentage of subjects with low, normal or high values.

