6.3.2 Causality Classification

The relationship between the drug and the occurrence of each adverse event will be assessed and categorised as below. The Investigator will use clinical judgement to determine the relationship. Alternative causes, such as natural history of the underlying disease, concomitant therapy, other risk factors etc will be considered. The Investigator will also consult en Investigator Brochure or other product information.

Not related: Temporal relationship of the onset of the event relative to the administration of the product, is not reasonable or another cause can by itself explain the occurrence of the event.

Unlikely: Temporal relationship of the onset of the event, relative to the administration of the product, is likely to have another cause which can by itself explain the occurrence of the event.

Possibly related: Temporal relationship of the onset of the event, relative to the administration of the product, is reasonable but the event could have been due to another equally likely cause.

Probably related: Temporal relationship of the onset of the event, relative to the administration of the product, is reasonable and the event is more likely explained by the product than any other cause.

Definitely related: Temporal relationship of the onset of the event, relative to the administration of the product, is reasonable and there is no other cause to explain the event or a re-challenge (if feasible) is positive.

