 resulted in death is/was life-threatening resulted in persistent or significant disability/incapacity required hospitalisation prolonged an ongoing hospitalisation resulted in a congenital anomaly or birth defect other – please specify* Please give further details in section 6 'Outcome'											
Maximum intensity (up	until	time of initial report)	М	lild 🗌			Modera	ate 🗌		Severe	e 🗌
Onset Date (when event became ser	ious)	Onset Time	E	nd date		End	time		OR	Duration	

Signature of person making report: _____

Date:/	/
--------	---

R&E use only: case reference number

To be completed by the person filling	a in i	the SAE form					
UHB R&D no.: SU/2006/2424		ubject ID/initials	1	Onset date of	SAE		
RESEARCH RELATED SAE/SUSAR INITIAL REPORT FORM (page 2 of 4)							
5. Details of IMP/device/intervention	on(s) if applicable (fu	urther sp	ace available in section			
Name of drug/device/intervention		Total daily d (if applicab		Dosing regime (inc route)	Date/time of last dose/intervention		
6. Outcome (further space available	e in s	section 12)	1				
Resolved*		Ongoing*	Die	d* (give cause and PM d	letails if available)		
*Give details:							
Was the patient withdrawn from the		-		Yes 🗌	No 🗌		
7. Location of (onset of) SAE (furth			section	12)			
Setting (e.g. hospital*, home, GP, nu	ırsın	g home):					
*If SAE occurred on UHB precinct gi	ve e	exact location:					
8. Action taken and further inform	atio	n (further space a	available	in section 12)			
Please describe action taken:							
Other information relevant to assess	mer	nt of case e.g. me	dical hist	tory, family history, test r	esults.		

R&E use only: case reference	number					
To be completed by the perso	n filling in the SAE form					
UHB R&D no.: SU/2006/24	424 Subject ID/initials	Onset date of SAE				
RESEARC	H RELATED SAE/SUSAR INITIAL R	EPORT FORM (page 3 of 4)				
	ess (to be completed by physician)					
Is the SAE related to the drug/device/intervention?	*If possibly, probably or definitely related, was the SAE unexpected?	In addition to this form, and within 5 days:				
Not related	☐ Yes ¹	1 - Please complete and return all				
Unlikely to be related		sections of the follow up report form.				
Probably related* Definitely related*	(Unexpected means not described					
	in the protocol or other product information)	sections 1, 2 and 3 of the follow up report form.				
For blinded studies:	mornation					
Has the randomisation code b	een broken in making this assessmer	nt: 🗌 Yes [*] 🗌 No				

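### The third treatment-emergent condition in section 8.4.4 omits the top level of the protocol's own causality scale, for pre-existing events of unchanged intensity only

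*Protocol*

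**What the plan says.** Section 8.4.4 (Safety Evaluation) defines a TEAE as an adverse event in the active phase that meets any one of three conditions:

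- Condition 1, a new event: "it was not present prior to receiving the first dose of IMP, or"
- Condition 2, a worsened event: "it was present prior to receiving the first dose of IMP but the intensity increased during the active phase of the study, or"
- Condition 3, an event present before the first dose for which "the intensity is the same but the drug relationship became possible or probable during the active phase of the study"

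The same section says that TEAEs are flagged with an asterisk in the listings, that the incidence of all adverse events, TEAEs and serious adverse events is tabulated, and that all safety data go into the subject listings.

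Section 6.3.2 (Causality Classification) sets the scale on which condition 3 depends. It has five levels: not related, unlikely, possibly related, probably related and definitely related. The last is reached when the timing of onset is reasonable and "there is no other cause to explain the event or a re-challenge (if feasible) is positive".

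The serious adverse event form in Appendix 4 takes the upper three levels together: "If possibly, probably or definitely related, was the SAE unexpected".

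**The concern.** Condition 3 is evidently meant to catch a pre-existing event that has not changed in intensity but has come to be attributed to the study drug. A rule of that kind should take in every level from a chosen threshold upward. This one names two of the three related levels and leaves out the strongest. It has no wording such as 'at least possible' that would bring in the top level by implication.

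As written, the rule is not monotone: for the same event, a firmer causal judgement can remove TEAE status that a weaker judgement would confer. That can hardly be intended. A programmer who applies the text literally leaves such an event unflagged, and one who follows the presumed intent departs from the protocol. Any resulting error runs one way, towards under-counting related TEAEs, in a study that has the safety of the subcutaneous route as a stated objective.

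**Working it through.** No arithmetic applies, and the protocol gives no figure to reproduce. The check sets the scale in section 6.3.2 against the conditions in section 8.4.4.

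**Step 1. Does each condition test causality?** Conditions 1 and 2 do not. Only condition 3 does, and it names possible and probable.

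**Step 2. Cross the event types with the causality levels.** Each cell shows whether the event is a TEAE on a literal reading, with the relationship re-assessed during the active phase.

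| Causality after re-assessment | New event | Pre-existing, intensity increased | Pre-existing, intensity unchanged |
|---|---|---|---|
| Not related | Yes (condition 1) | Yes (condition 2) | No |
| Unlikely | Yes (condition 1) | Yes (condition 2) | No |
| Possibly related | Yes (condition 1) | Yes (condition 2) | Yes (condition 3) |
| Probably related | Yes (condition 1) | Yes (condition 2) | Yes (condition 3) |
| Definitely related | Yes (condition 1) | Yes (condition 2) | **No** |

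Only one cell is anomalous, the bottom right. Condition 3 covers two of the three related levels.

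**Step 3. Does another section repair it?** No. The Appendix 4 form puts possibly, probably and definitely related in one group, which supports the view that the omission in section 8.4.4 is an oversight. The form governs the assessment of serious events, though, and does not amend the TEAE definition.

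**Step 4. Can the cell be reached?** In principle it can:

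- Section 6.2.2 counts adverse events from informed consent, and Table 2 allows Screening up to a month before Day 0. Events can therefore precede the first dose, and section 8.4.1 expects pre-treatment events.
- Section 6.3.7 requires continuing events to be reviewed at each later assessment, so the causality judgement may change while the intensity does not.
- The re-assessment has to go straight to definitely related. An event judged possibly or probably related during the active phase and upgraded later has already met condition 3.

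**Step 5. What does an affected event lose?** It loses the asterisk in the listings and its place in TEAE counts. It stays in the tabulation of all adverse events and in the listings. If it is serious, section 6.4.1 requires it to be reported whatever its relationship to the drug.

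**The case against.** The strongest objection is that the anomalous cell is nearly empty under the protocol's own definitions. The top level begins: "Definitely related: Temporal relationship of the onset of the event, relative to the administration of the product, is reasonable". An event that started before the first dose and has not worsened has an onset that precedes administration and, usually, an evident origin other than the drug. It will hardly ever be judged definitely related. This stands, and it is why the point is small. It does not make the rule right. The same onset wording opens the two levels that condition 3 does name ("Possibly related: Temporal relationship of the onset of the event, relative to the administration of the product, is reasonable" and "Probably related: Temporal relationship of the onset of the event, relative to the administration of the product, is reasonable"), so it is no reason to include those two and exclude the third.

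A second objection is that nothing disappears from the report and no efficacy result or decision rests on the flag. This also stands, and it limits the consequence to TEAE classification.

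Three stronger readings are tempting, and the protocol does not support them:

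- *That definitely related events in general are not treatment-emergent.* Conditions 1 and 2 carry no causality test, so every such event that is new or worsened is a TEAE.
- *That the drug-relationship tables would lose the events most clearly linked to the drug.* Section 8.4.4 does not say that the relationship summary is restricted to TEAEs, and it tabulates all adverse events.
- *That the second injection is a built-in re-challenge, so the top level will often be reached.* The protocol never calls it one. It is a different formulation (11.25 mg, three-month), given one month after a one-month sustained-release injection with no planned washout. A pre-existing event that simply persists at the same intensity does not show resolution followed by recurrence. Injection-site pain, redness and swelling, the reactions most likely to repeat with each injection, cannot pre-date the first injection and so qualify under condition 1.

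**Conclusion.** The point holds in a narrow form. Condition 3 in section 8.4.4 is out of step with the five-level scale in section 6.3.2. Since the protocol states the rule in full, this is an inconsistency in the text and not a detail left for a later analysis plan.

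Its reach is limited to pre-existing adverse events of unchanged intensity that are re-assessed directly as definitely related. The effect is confined to the TEAE flag and TEAE counts, and any error is towards under-counting. The protocol does not allow the number of affected events to be estimated. It is probably very small and possibly none.

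This conclusion rests on two assumptions: that condition 3 is applied literally, and that causality is recorded on the scale in section 6.3.2. The correction is worth making because it is so easy, but it is a minor, near-editorial matter.

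**What to change.** In the third condition of section 8.4.4, add the definite level to the two already named, so that a pre-existing event of unchanged intensity is treatment-emergent when its relationship becomes possible, probable or definite during the active phase. The condition then covers all three related levels in section 6.3.2 and agrees with the grouping on the Appendix 4 form.

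The cost is a few words in the protocol and the same change in any programming specification that derives the TEAE flag. Data collection, sample size, the efficacy analysis and clinical procedures are unaffected.

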8.5 Interim Analyses and Data Monitoring

An interim number of treatment failures will be recorded. If this number reaches 6 or more recruitment will be closed and a data monitoring committee will be convened.

9. COMPLIANCE WITH GCP & ETHICAL CONSIDERATIONS

The study will be performed subject to Research Ethics Committee (REC) approval, including any provisions of Site Specific Assessment (SSA), and local Research and Development (R&D) approval.

This study will be conducted in accordance with:

• The Medicine for Human Use (Clinical Trials) Regulations 2004.

• International Conference for Harmonisation of Good Clinical Practice (ICH GCP) guidelines

• Research Governance Framework for Health and Social Care.

Monitoring and Audit

The study will be subject to monitoring and audit in accordance with UHB policy. All trial related documents will be made available on request for monitoring and audit by UHB, the relevant Research Ethics Committee and for inspection by the Medicines and Healthcare products Regulatory Authority or other licensing bodies.

10. DATA HANDLING AND RECORD KEEPING

The Investigator is to report all data with respect to protocol procedures, drug administration, laboratory data, safety data and efficacy data in the patients' medical records in addition to any study specific forms.

Study documents (paper and electronic) will be retained in a secure location during and after the trial has finished. All source documents will be retained for a period of 15 years following the end of the study. Where trial related information is documented in the medical records those records will be identified by a 'Do not destroy before dd/mm/yyyy' label where date is 15 years after the last patient last visit.

11. INDEMNITY

This is an NHS sponsored research study. For NHS sponsored research HSG(96)48 reference no.2 refers. If there is negligent harm during the clinical trial when the NHS body owes a duty of care to the person harmed, NHS indemnity covers NHS staff, medical academic staff with honorary contracts, and those conducting the trial. NHS Indemnity does not offer no-fault compensation and is unable to agree in advance to pay compensation for non-negligent harm. Ex-gratia payments may be considered in the case of a claim.

12. FINANCE

This study is funded by a grant from IPSEN. The grant will cover the cost of the trial including research clinic staff time (trial research nurse and research fellow), pharmacy dispensing costs and the costs of laboratory tests. Patients will not be paid for their involvement in the study but travel expenses to and from research outpatient clinics will be paid.

APPENDIX 1 TNM STAGING

TNM Classification System (T)

TX Primary tumor cannot be assessed T0 No cancer detected T1 Clinically inapparent tumor-not palpable or visible by imaging T1a Tumor found incidentally; takes up < 5% of prostate tissue T1b Tumor found incidentally; takes up > 5% of prostate tissue T1c Tumor identified by prostate needle biopsy because of elevated PSA T2 Palpable tumor confined within the prostate T2a Tumor involves < 50% of 1 prostate lobe T2b Tumor involves > 50% of 1 prostate lobe T2c Tumor involves both lobes T3 Palpable tumor extending through prostate capsule and/or seminal vesicle(s) T3a Unilateral extracapsular extension T3b Bilateral extracapsular extension T3c Tumor invades seminal vesicle(s) T4 Tumor is fixed or invades adjacent structures other than the seminal vesicles T4a Tumor invades bladder neck and/or external sphincter and/or rectum T4b Tumor invades other areas near prostate

TNM Classification System (N)

N+ Involvement of regional lymph nodes (LN) NX Regional LN cannot be assessed N0 No regional LN metastases N1 Cancer has spread to 1 LN, (<2 cm) N2 Cancer has spread to 1 or more LN, (2-5 cm) N3 Cancer has spread to at least 1 LN, (>5 cm)

TNM Classification System (M)

M+ Distant metastatic spread MX Presence of distant metastases cannot be assessed M0 No distant metastasis M1 Distant metastasis M1a Involvement of non regional lymph nodes M1b Involvement of bone(s) M1c Involvement of other distant sites

APPENDIX 2: Drugs not permitted by the study protocol:

Anabolic steroids **Barbiturates** Betamethasone (unless patient has been stable on this drug for more than 3 months) Bicalutamide Carbamazepine (unless patient has been stable on this drug for more than 3 months) Chlorpromazine (unless patient has been stable on this drug for more than 3 months) Cimetidine Clomiphene Cyproterone Acetate (except when given as anti-flare medication with the first injection) Deflazacort Dexamethasone (unless patient has been stable on this drug for more than 3 months) Diethylstilboestrol Digoxin (unless patient has been stable on this drug for more than 3 months) Dutasteride Finasteride Fluphenazine Flutamide Gabapentin (unless patient has been stable on this drug for more than 3 months) Gonadorelin Gonadotropin Goserelin Hydrocortisone (unless patient has been stable on this drug for more than 3 months) Ketoconazole (topical use is allowed) Lamotrigine Leuprorelin Levetiracetam Mesterolone Methotripmeprazine Methylprednisolone Metoprolol Metyrapone Pericyazine Perphenazine Phenobarbital Phenytoin (unless patient has been stable on this drug for more than 3 months) Pipotiazine Prochlorperazine (unless patient has been stable on this drug for more than 3 months) Promazine Sodium Valproate (unless patient has been stable on this drug for more than 3 months) Spironolactone Testosterone Tetracycline Thioridazine Tiagabine Topiramate Trifluoperazine Vigabatrin
APPENDIX 3: SUMMARY OF PRODUCT CHARACTERISTICS

SUMMARY OF PRODUCT CHARACTERISTCS: DECAPEPTYL SR 3MG

1. NAME OF THE MEDICINAL PRODUCT

DECAPEPTYL SR 3mg, powder for suspension for injection

2. QUALITATIVE AND QUANTITATIVE COMPOSITION

Triptorelin (I.N.N.) 4.2 mg, as triptorelin acetate. The vial contains an overage to ensure that a dose of 3mg is administered to the patient.

For excipients, see 6.1.

3. PHARMACEUTICAL FORM

Powder for suspension for injection, sustained release formulation.

4. CLINICAL PARTICULARS

4.1 Therapeutic indications

Treatment of patients with locally advanced, non-metastatic prostate cancer, as an alternative to surgical castration (see section 5.1).

Treatment of metastatic prostate cancer.

Treatment of endometriosis.

Treatment of uterine fibroids prior to surgery or when surgery is not appropriate

4.2 Posology and method of administration

Prostate cancer

One intramuscular injection should be administered every 4 weeks (28 days). No dosage adjustment is necessary in the elderly.

Endometriosis and uterine fibroids

One intramuscular injection every 28 days. For the treatment of endometriosis and uterine fibroids the treatment must be initiated in the first five days of the cycle. The maximum duration of treatment should be 6 months. For patients with uterine fibroids DECAPEPTYL SR 3mg should be administered for a minimum of 3 months.

A second course of treatment by DECAPEPTYL SR 3mg or by other GnRH analogues should not be undertaken due to concerns about bone density losses.

4.3 Contraindications

Hypersensitivity of GnRH analogues or to any of the excipients.

In prostate cancer, DECAPEPTYL SR 3mg should not be prescribed in patients presenting with spinal cord compression or evidence of spinal metastases.

In endometriosis and uterine fibroid treatment, confirm that the patient is not pregnant before beginning treatment.

4.4 Special warnings and precautions for use

Prostate cancer

Initially, DECAPEPTYL 3mg causes a transient increase in serum testosterone and consequent worsening of symptoms including increase in bone pain (and acid phosphatase levels). Consideration should be given to the use of an anti-androgen for three days prior to DECAPEPTYL SR 3mg treatment, to counteract this initial rise in serum testosterone levels. During the first month of treatment, patients presenting with, or at particular risk of developing, ureteric obstruction should be carefully monitored, as should those at risk of developing spinal cord compression. Continued treatment with DECAPEPTYL SR 3mg leads to suppression of testosterone (and dihydrotestosterone) and consequent improvement in the disease.

Endometriosis and uterine fibroids

Regular administration, every 28 days of one vial of DECAPEPTYL SR 3mg causes a persistent hypogonadotrophic amenorrhoea. During the first month of treatment, a non-hormonal contraception should be given. A supervening metrorrhagia in the course of treatment, other than in the first month, should lead to measurement of plasma oestradiol levels. Should this level be less than 50 pg/mL, possible associated organic lesions should be sought. After withdrawal of treatment, ovarian function resumes and ovulation occurs on average 58 days after the last injection, with first menses occurring on average 70 days after the last injection. Contraception may therefore be required. Due to concerns about bone density losses, DECAPEPTYL SR 3mg should be used with caution in women with known metabolic bone disease.

4.5 Interaction with other medicinal products and other forms of interaction

Drugs which raise prolactin levels should not be prescribed concomitantly as they reduce the level of LHRH receptors in the pituitary.

4.6 Pregnancy and lactation

Reproductive studies in primates have shown no maternal toxicity or embryotoxicity, and there was no effect on parturition. Inadvertent administration of triptorelin during human pregnancy has not demonstrated a teratogenic or other foetal risk. However, it is recommended that DECAPEPTYL SR 3mg should not be used during pregnancy or lactation.

4.7 Effects on ability to drive and use machines

There is no evidence that DECAPEPTYL SR 3mg has any effect on the ability to drive or operate machinery.

